### **Sub-Study Visits.**

**Recruitment/Screening (Visit 1, Screening & Scheduling).** Eligible participants who complete the screening survey will be given a chance to review the consent form. Study staff will provide the participant with ample time to review the study information and ask questions related to their participation. Participants who enroll will be scheduled to return for a baseline visit (typically within the next 7 days). The Homeless Shelter Alliance case workers, who work

with the shelter's guests, may encourage their clients to enroll and retain participation in the study.

**Baseline (Visit 2).** Enrolled participants will be randomly assigned to the EC or FI + EC condition. Enrolled participants will be asked to provide their personal information (name and phone numbers). Participants will be instructed to switch from combustible cigarettes to e-cigarettes at bedtime or 10:00 pm (whichever occurs first), on the evening prior to their next scheduled weekly session. They will be provided with a EC device and they will have the opportunity to try it out. They will be provided with 7 pods (5% nicotine).. They will keep the pods in order to practice using the e-cigarette device over the week prior to their switch date. Participants will be advised about earning financial incentives for switching to ECs or yoking) beginning the following week on the quit/switch day. The schedule of payments will be discussed with all participants (see Table 1). Participants will be instructed not to use THC-containing vaping products and "street" vaping products, and not to modify or add chemicals to their vaping supplies while they are enrolled in the study. They will be counseled to use only the supplies that they are given by study staff, and to avoid dual use of e-cigarettes and cigarettes or other combustible products, including marijuana. Participants will receive a \$10 Greenphire clincard paymentfor completing this visit and they will be provided with a Tracfone (or similar "burner" phone) along with a prepaid phone plan that will cover the study period to facilitate communication between the participant and study staff. Participants will be encouraged to complete this visit as soon as possible, but it can be completed within 21 days of visit 1. Enrollment into the sub-study will cease once 60 participants are enrolled.

**Switch Day (Visit 3; 1 week after baseline).** Participants will complete self-report questionnaires on a laptop computer; and expired CO and weight will be measured in a private area of the shelter to ensure confidentiality. Participants assigned to the FI + EC treatment will receive an additional \$20 paymentif their expired CO level is  $\leq 8$  ppm (please note that the less stringent cut-off of 8 ppm will be used to verify abstinence on the first post-switch day only, because of the recency of switching). EC participants will receive the same payment as their yoked FI + EC counterpart. Attempts will be made to contact participants who do not attend study visits, in order to obtain self-reported smoking status. Participants will be supplied with pods in the flavor(s) of their choice, based off of what research staff has available, and based on their pre-switch smoking level.

**1-4 Weeks Post-Switch (Visits 4-7).** Participants will complete self-report questionnaires on a laptop computer; and expired CO and weight will be measured in a private room to ensure confidentiality. Participants randomized to the + EC group will receive an additional \$20-\$40 credit for self-reported abstinence and CO readings  $\leq 6$  ppm. EC participants will receive the same payment as their yoked FI + EC counterpart. Additional pods will be provided at each weekly visit based on pre-switch smoking levels. Participants will be

provided with 1 additional e-cigarette device *only if* they lose or damage the first device. Participants will not be provided with any e-cigarette supplies after visit 7, to determine whether they continue to use the e-cigarette on their own.

**8 Weeks Post-Switch (Visit 8).** Participants will complete self-report questionnaires on a laptop computer; and expired CO and weight will be measured in a private area to ensure confidentiality. Participants will receive a \$50 for completing this final follow-up visit, and participants may keep their study phones. Participants will be advised that they can receive free smoking cessation treatment through the Tobacco Treatment Research Program^36 or the Oklahoma Tobacco Helpline and provided with contact information.

**Table 1. Sub-study compensation schedule.**

	Assessments	Incentive/ Yoking	Total Possible Earnings
Visit 1 (Brief Screening)	\$0	\$0	\$0
Visit 2 (baseline/enrollment; 1 week pre-switch)	\$20	\$0	\$20
Visit 3 (switch Day)	\$20	\$20	\$40
Visit 4 (1-week post-switch)	\$20	up to \$25	\$45
Visit 5 (2 weeks post-switch)	\$20	up to \$30	\$50
Visit 6 (3 weeks post-switch)	\$20	up to \$35	\$55
Visit 7 (4 weeks post-switch)	\$20	up to \$40	\$60
Visit 8 (8 weeks post-switch)	\$50	\$0	\$50
Total Possible Earnings	\$170	\$150	\$320

### **E. Statistical Methods**

**Survey Study.** Day shelter guests (up to 1000) using shelter services will have the opportunity to participate in the survey study. Study staff will enroll unique participants each month (i.e., participants may participate only once). Descriptive statistics will be generated (e.g., frequencies, means) to describe the characteristics, needs, tobacco use history, and tobacco treatment preferences of study participants, along with correlation and regression analyses to identify cross-sectional relationships among variables. For example, we will examine the percent of individuals who have used e-cigarettes as a means of quitting smoking as well as the percent who are interested in switching to e-cigarettes in the future. Tobacco use history and preferences for tobacco cessation treatment will be described (e.g., means, frequencies). The relations between tobacco use and health, other health behaviors, sociodemographic (e.g., education, race/ethnicity, gender), and personal characteristics (e.g., stress and mental health) will be examined via correlation and regression analyses. The rate of missing data and missing data patterns will be examined before analysis. If the combined missing rate is very small, say less than 5%, then we may safely perform the data analysis on the available data. If the missing rate is high, then we will explore sequential multiple imputation (SMI) as described by Raghunathan et al. The analysis results from SMI data will be compared with those from the available data.

**Sub-Study.** A sub-sample of survey participants ( $N = 60$ ) who are currently smoking cigarettes will be randomized to one of two intervention groups and followed for ten weeks (2-weeks pre-switch through 8-weeks post-switch). This pilot study will provide feasibility data and intervention effect sizes for the power analysis for a future fully-powered randomized controlled trial. Descriptive statistics will be employed (e.g., frequencies, means) to characterize combustible cigarette cessation, cigarette reduction, daily EC use, and dual EC and combustible cigarette use. The intervention groups will be compared on CO-verified cigarette abstinence at 4 and 8 weeks after a scheduled switch attempt using logistic regression analysis. Secondary analyses will focus on reductions in cigarette smoking, EC use/switching, and dual use of ECs and combustible cigarettes.

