### **Sub-Study.**

Overview. The sub-study will examine the feasibility and preliminary efficacy of providing financial incentives for combustible cigarette abstinence in combination with switching to e-cigarettes among 60 socioeconomically disadvantaged Homeless Alliance day shelter users. A total of 60 adults who access the day shelter will be recruited to participate in the sub-study. Participants will be randomly assigned to one of two groups and followed weekly from 1 week prior to switching through 4 weeks after switching, with a final 8-week post-switch follow-up. The intervention groups are 1) switching to e-cigarettes (EC), or 2) small financial incentives for cigarette abstinence + switching to e-cigarettes (FI + EC). Payments will be made via Greenphire clincard, which is similar to a debit card. The primary outcome will be carbon monoxide (CO)-verified combustible cigarette abstinence (CO) at 4- and 8-weeks post-switch date. Combustible cigarette reduction, EC use/switching, and dual use (cigarettes and ECs) will also be examined.

**Intervention Groups.** All participants will have the opportunity to earn \$20 for completing study assessments at visits 2 through 7 and \$50 for completing visit 8 (see Table 1).

Financial Incentives + E-Cigarettes (FI + EC). At baseline (1-week pre-switch), participants assigned to this group will be provided with an e-cigarette device and they will be offered 7 pods to try. Participants will be encouraged to practice using the device over the subsequent week (before they switch to exclusive use). Participants will be advised to completely switch from combustible cigarettes to

the e-cigarette device one week after the baseline visit. On the switch date, they will be supplied with refill cartridges in the flavor(s) of their choice and based on their pre-switch smoking level. One pod ≈ 200 puffs and provides the amount of nicotine in ≈ 1 pack of cigarettes. Thus, someone who smokes a pack of cigarettes each day may be expected to use about 1 pod per day.

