#### **G. Human Participants**

- Participant Population.** The overall survey study will include up to 1000 individuals recruited from the Homeless Alliance day shelter. Interested individuals may be included in the study if they: 1) are able to speak and understand English 2) are  $\geq 18$  years of age. The Day Shelter primarily offers services to adults, and rarely children. Children and families are referred to other locations that are safer for children (e.g., where individuals are screened for felonies and sex offenses). The sub-study will include 60 individuals who meet the sub-study inclusion criteria: 1)  $\geq 21$  years of age (verified by state driver's license or ID card), 2) have an expired CO level  $\geq 8$  ppm suggestive of current smoking, 3) report currently smoking  $\geq 5$  cigarettes per day, 4) willing and able to attend 8 study visits over an 10 week period (2 weeks pre-switch through 8 weeks post-switch), 5) interested in switching from smoking cigarettes to e-cigarettes, 6) willing to abstain from smoking marijuana/cannabis and other combustible tobacco products for the duration of the study, 7) able to speak and understand English, 8) demonstrates  $> 6^{\text{th}}$  grade English literacy by earning a score  $\geq 4$  on the Rapid Estimate of Adult Literacy in Medicine-Short Form (REALM-SF; i.e., required to complete tablet/laptop questionnaire items), 9) is able to read a 3-sentence selection from the consent form, and 10) is not pregnant or breast feeding or planning to become pregnant. Individuals may be excluded from participation based on professional judgement in situations that would interfere with study participation such as apparent alcohol or other substance intoxication, uncontrolled psychosis, cognitive impairment, verbal or physical aggression directed towards study staff or other guests, or other extreme situations. New participants who approach the study team and participants who completed

the primary survey in the past (pre-COVID – Before March 2020; before the start of the sub-study) may participate in the sub-study if they currently meet eligibility criteria. Going forward, potential participants will only be screened once for the sub-study and the CitiCare ID Number will be referenced to verify that the participant has not been screened more than once. Due to the targeted population, bus passes may be provided at visits to assist participants in coming back to their next appointment.

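### The primary logistic comparison of abstinence names no baseline covariate, although smoking level is recorded before randomisation; pre-specifying one would be a cheap, modest improvement

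*Combined protocol and SAP*

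**What the plan says.** The Sub-Study overview defines the endpoint: "The primary outcome will be carbon monoxide (CO)-verified combustible cigarette abstinence", assessed 4 and 8 weeks after the switch date. The whole specification of the primary model is one sentence in Section E: "The intervention groups will be compared on CO-verified cigarette abstinence at 4 and 8 weeks after a scheduled switch attempt using logistic regression analysis". No covariate is listed, and nothing says whether the model is adjusted or unadjusted.

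On design, "A total of 60 adults who access the day shelter will be recruited to participate in the sub-study", and at the baseline visit "Enrolled participants will be randomly assigned to the EC or FI + EC condition". The documents give no allocation ratio, stratification or minimisation.

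Smoking level is available before randomisation. Section G requires that participants "have an expired CO level" of at least 8 ppm and "report currently smoking" at least 5 cigarettes per day. Smoking level also sets the pod supply: "Additional pods will be provided at each weekly visit based on pre-switch smoking levels".

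Section E gives the pilot two purposes: feasibility data, and effect sizes for the power analysis of a later, larger trial.

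**The concern.** How heavily someone smokes plausibly affects the chance of giving up cigarettes. In two arms of about 30, chance alone can leave one arm with noticeably heavier smokers. As written, neither the randomisation nor the analysis takes account of this. An unadjusted estimate from an unlucky allocation would then carry part of that difference into the effect size passed to the next trial's power calculation.

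The silence has a second cost. If covariates are not named in advance, the choice to adjust, and for what, can be made after the outcome data are seen.

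**Working it through.** **Figure to reproduce.** None. N = 60 is given without alpha, power, assumed abstinence rates or an effect size.

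**Inputs.** From the documents: N = 60, two arms, a binary outcome, logistic regression. Assumed: 30 per arm (compatible with yoking each EC participant to an FI + EC participant), the abstinence rates, and the odds ratio for abstinence per SD of baseline smoking. The documents supply none of these assumed values.

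**1. How often imbalance arises.** The SD of the standardised baseline difference is sqrt(1/30 + 1/30) = 0.258.
- P(difference > 0.25 SD) = 33%.
- P(difference > 0.4 SD): 0.4/0.258 = 1.55, two-sided tail 12.1%.
- P(difference > 0.5 SD) = 5%.

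**2. Average shift in the 12% of allocations above 0.4 SD.** The mean absolute imbalance there is 0.258 × φ(1.55)/(1 − Φ(1.55)) = 0.258 × 0.120/0.0607 ≈ 0.51 SD. To first order, shift in risk difference ≈ |ln OR| × imbalance × mean of p(1 − p) over the arms. The marginal rates used here make this slightly too large.

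| Rates | mean p(1−p) | OR 0.6 (abs. ln 0.511) | OR 0.4 (abs. ln 0.916) |
|---|---|---|---|
| 30% v 10% | (0.21+0.09)/2 = 0.150 | 3.9 points | 7.0 points |
| 40% v 15% | (0.24+0.1275)/2 = 0.184 | 4.8 points | 8.6 points |
| 20% v 5% | (0.16+0.0475)/2 = 0.104 | 2.7 points | 4.9 points |

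Simulation at 30% v 10%, 40% v 15%, 40% v 10% and 20% v 20% gave mean shifts of about 3 to 5 points at OR 0.6 and about 6 to 8 points at OR 0.4. After adjustment the mean shift was within about 1 point.

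**3. What adjustment gains over all allocations (simulated).**
- Variance of the standardised risk difference relative to the raw difference: a fall of about 5-11% at OR 0.4; ratio about 0.98-1.01 at OR 0.6; about 1.01-1.02 when the covariate is weak (OR 0.8) or unrelated.
- Power: about +3 to +4 points at OR 0.4, little change at OR 0.6, and a loss of about 1 to 2 points if unrelated.
- Mean SE of the log odds ratio at 30% v 10%: 0.785 unadjusted; 0.821 adjusted at OR 0.6 (0.821/0.785 = 1.046, up 5%); 0.867 at OR 0.4 (0.867/0.785 = 1.104, up 10%).

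**4. Typical error, as opposed to mean shift.** In allocations above 0.4 SD at 30% v 10%, the mean absolute error of the risk difference was 8.1 points unadjusted and 7.9 adjusted at OR 0.6, and 9.2 and 7.8 at OR 0.4.

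**5. Sparse cells.** With 5% abstinence in one arm, P(no abstainers among 30) = 0.95^30 = 21%. Ordinary maximum likelihood then has no finite estimate, with or without a covariate. The simulations agree: 21-22% of fits at 20% v 5% were not estimable. At 10% in the lower arm the figure is 0.90^30 = 4%.

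**The case against.** The case against is substantial, and most of it stands.

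- **Silence is not a decision.** A reader might infer that the plan chose an unadjusted analysis. Section E neither plans nor excludes covariates; it supports only the statement that none is specified.
- **Chance imbalance is not bias.** Randomisation keeps the unadjusted comparison valid, and its interval allows for imbalance on average. The shift at issue is conditional on an unlucky allocation. At OR 0.6 it is less than half of the roughly 10-point SD of the risk difference.
- **Precision.** A reader might infer that leaving out the covariate costs precision in the planned analysis. For the log odds ratio the reverse holds, because adjustment raises its SE and changes the target to a conditional odds ratio. Any precision gain belongs to the standardised risk difference, which the plan does not mention.
- **Accuracy.** A reader might take the mean shift after adjustment, within about 1 point, to mean that the adjusted estimate is accurate to 1 point. Step 4 shows a typical error near 8 points either way.
- **Prognostic strength is unknown.** The documents do not say how well smoking level predicts abstinence. If it predicts weakly, there is no gain or a slight loss.
- **Timing.** On the switch date "they will be supplied with refill cartridges in the flavor(s) of their choice and based on their pre-switch smoking level", a week after randomisation and after devices have been issued. That level might be a post-randomisation value, so only the screening measurements in Section G are clearly safe as covariates.

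What survives is that a plausible predictor is collected on everyone before randomisation, nothing balances it, and its use is left open in an analysis meant to supply an effect size.

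**Conclusion.** The point holds as a cheap improvement, optional to modest in importance, and not as a flaw that undermines the trial. The primary model names no covariate and no stratification is stated. About one allocation in eight would show a baseline difference above 0.4 SD. In those, a clearly prognostic covariate (OR 0.6 to 0.4 per SD) would shift the unadjusted risk difference by roughly 3 to 8 points on average, and by less at abstinence rates as low as 20% v 5%. Averaged over all allocations, the effect of adjustment is small and can go slightly the wrong way.

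These sizes rest on 1:1 allocation, an approximately normal covariate, assumed abstinence rates and assumed prognostic strength. Feasibility is a stated aim alongside the effect sizes, so the abstinence contrast is not the pilot's only product. The sparse-cell problem is separate: adjustment neither causes nor cures it, but it should be settled in the same sentence.

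**What to change.** In Section E, Sub-Study:

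1. Fit each abstinence model (weeks 4 and 8) with arm plus one pre-specified covariate measured before randomisation: screening cigarettes per day, on the log scale. State that it is the screening value, not the level used later to set pod supply.
2. Report the adjusted odds ratio, described as conditional, together with the risk difference standardised over the randomised participants and its confidence interval.
3. Keep the unadjusted comparison as supportive.
4. Name a method for sparse cells, for example Firth's penalised likelihood, to be used whether or not the covariate is included.

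The cost is a sentence or two, with no new data. The downsides are one more parameter in a 60-person model, a larger SE for the log odds ratio, an odds ratio that is no longer marginal, and a small loss (variance up about 1-2%, power down about 1-2 points) if smoking level turns out not to predict abstinence.

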#### **F. Gender/Minority/Pediatric Inclusion for Research**

The study has no inclusion/exclusion criteria based on gender or race/ethnicity. Children  $< 18$  years of age will be excluded from participation in the survey study. Children and young adults  $< 21$  years of age will be excluded from the sub-study because tobacco products are only legally available to adults 21 years and older.

#### **G. Human Participants**

- Participant Population.** The overall survey study will include up to 1000 individuals recruited from the Homeless Alliance day shelter. Interested individuals may be included in the study if they: 1) are able to speak and understand English 2) are  $\geq 18$  years of age. The Day Shelter primarily offers services to adults, and rarely children. Children and families are referred to other locations that are safer for children (e.g., where individuals are screened for felonies and sex offenses). The sub-study will include 60 individuals who meet the sub-study inclusion criteria: 1)  $\geq 21$  years of age (verified by state driver's license or ID card), 2) have an expired CO level  $\geq 8$  ppm suggestive of current smoking, 3) report currently smoking  $\geq 5$  cigarettes per day, 4) willing and able to attend 8 study visits over an 10 week period (2 weeks pre-switch through 8 weeks post-switch), 5) interested in switching from smoking cigarettes to e-cigarettes, 6) willing to abstain from smoking marijuana/cannabis and other combustible tobacco products for the duration of the study, 7) able to speak and understand English, 8) demonstrates  $> 6^{\text{th}}$  grade English literacy by earning a score  $\geq 4$  on the Rapid Estimate of Adult Literacy in Medicine-Short Form (REALM-SF; i.e., required to complete tablet/laptop questionnaire items), 9) is able to read a 3-sentence selection from the consent form, and 10) is not pregnant or breast feeding or planning to become pregnant. Individuals may be excluded from participation based on professional judgement in situations that would interfere with study participation such as apparent alcohol or other substance intoxication, uncontrolled psychosis, cognitive impairment, verbal or physical aggression directed towards study staff or other guests, or other extreme situations. New participants who approach the study team and participants who completed

the primary survey in the past (pre-COVID – Before March 2020; before the start of the sub-study) may participate in the sub-study if they currently meet eligibility criteria. Going forward, potential participants will only be screened once for the sub-study and the CitiCare ID Number will be referenced to verify that the participant has not been screened more than once. Due to the targeted population, bus passes may be provided at visits to assist participants in coming back to their next appointment.

2. **Sources of Research Material.** Demographic, psychosocial, environmental and behavioral data will be collected via traditional self-report questionnaires completed in-person on password protected and encrypted OUHSC laptop or tablet computers. Expired CO will be collected to confirm self-reported smoking status. Height and weight will be collected. Attendance will be noted by the research staff each week for sub-study participants. Sub-study participants may be contacted by phone to assess tobacco use status if they do not attend in-person follow-up sessions.
3. **Recruitment and Informed Consent.** Participants will be recruited by study staff when they access services as the Homeless Alliance Day Shelter. The Homeless Shelter Alliance case workers, who work with the shelter's guests, may encourage their clients to enroll and retain participation in the study. Individuals will be provided with detailed information about the study, allowed as much time as needed to review the consent form, and given the opportunity to have their questions answered by knowledgeable research staff. Individuals may participate at a later date if they would like to give their participation further consideration. Written informed consent will be obtained from those who are interested in participating in the sub-study. The parent survey study requires a waiver of informed consent because the parent survey is anonymous. Instead, participants will review a cover letter that briefly describes the survey study and invites them to participate.
4. **Risks.** Participation in this study poses minimal risk to participants. However, one potential, although unlikely, risk to participants is loss of confidentiality. The severity of harm in the case of loss of confidentiality may range from mild to severe depending upon the individual and the specific circumstances. However, the risks of participation in the study are comparable to participation in standard tobacco cessation treatment, as loss of confidentiality may be experienced in either case.

